Magnetic resonance imaging (MRI) has proven a valuable tool in the detection, localization, and staging of prostate cancer (PCa). Multiparametric MRI, with diffusion weighted imaging (DWI) and dynamic contrast enhanced (DCE) perfusion imaging, is approximately 80% accurate for the detection of significant PCa in the prostate, and performs similar to computed tomography (CT) and radionuclide bone scan for detection of metastases. However, recent studies have found that conventional MRI has intermediate sensitivity for a patient's status regarding nodal metastases. Positron emission tomography (PET), on the other hand, has the potential to be the most sensitive imaging modality for whole body surveys of metastatic disease, depending on the radiopharmaceutical utilized. Fluorodeoxyglucose (FDG), which measures glucose metabolism and is the most widely utilized PET tracer, is sensitive for most cancers, but not PCa. New, specific PET tracers, which target the extracellular domain of prostate specific membrane antigen (PSMA), have shown similar to superior performance compared with MRI in the detection of metastatic disease and potentially similar performance to MRI for characterization of cancer in the gland. The advent of combination PET-MRI scanners allows for direct comparison of these two techniques, allowing the characterization of the performance of each, and their combination, for the detection and grading of prostate cancer in a number of scenarios, from presumed organ-confined disease for which focal therapy is planned, where accurate measurement of the extent of disease is crucial, to management of advanced disease and biochemical recurrence, where understanding the location and distribution of metastatic lesions could guide radiation therapy. The purpose of this study is to not only compare the sensitivity and specificity of both modalities, but to demonstrate the superiority of 68Ga-PSMA-HBED-CC PET to MRI for sensitivity, and its non-inferiority for specificity.

STUDY DESIGN

This is a multi-reader methodological study comparing the diagnostic value of 68GaPSMA-HBED-CC PET/CT or 68Ga-PSMAHBED-CC PET/MRI over MRI alone, using histologic confirmation or serial follow-up for up to 3 years as the gold standard for determination of primary prostate cancer or prostatic cancer recurrence/metastasis. Patients at moderate- to high-risk for metastatic disease who are scheduled for (the below outlines the patient cohorts recruited for this study): 1. High risk primary disease with planned surgical extirpation and lymph node dissection (oligometastatic disease) 2. Presumed intermediate or high-risk primary disease with planned targeted prostate biopsy 3. Conventional imaging equivocal or suggestive of metastatic disease, with planned biopsy of presumed metastasis a) PSA less than 0.5 ng/mL b) PSA greater than 0.5 ng/mL 4. Planned focal therapy of intermediate- to high-risk primary lesion. 5. Elevated PSA with no conventional imaging suggestive of metastatic or recurrent disease a) PSA less than 0.5 ng/mL b) PSA greater than 0.5 ng/mL. The purpose of the study is to compare 68Ga-PSMA-HBED-CC PET to conventional MRI. We hypothesize that this will demonstrate the superiority of 68Ga-PSMA-HBED-CC PET to MRI for sensitivity, and the non-inferiority of 68Ga-PSMA-HBED-CC PET to MRI for specificity. This is a paired, case-control design that is appropriate to statistically evaluate the difference in sensitivity and specificity between the two imaging modalities. Therefore, the estimation of Therefore, the estimation of population prevalence is not a study objective, and estimation of clinical utility through calculation of positive and negative predictive

values is not appropriate. Imaging studies and follow up subject scans will be organized so that a panel of independent readers will evaluate the MRI and PET studies to assess the level of suspicion for prostate cancer (see attached statistical methods for more details). The imaging data will be encoded and archived within IDEAL. The non-imaging data collected will be encoded and archived in a RedCap database. Participants will have 1-2 visits. During visit 1 they will receive a single IV dose of 68Ga-PSMA-HBED-CC (study drug) followed by either a PET/MRI scan or, in the event that an MRI cannot be performed concurrently and/or the subject has already undergone an MRI of the abdomen/pelvis or pelvis only, a PET/CT scan 1-3 hours after injection. The PET/MRI will be a combination of standard of care and research (the MRI portion is standard of care but the PET is for research only). The PET/CT scan will be for research purposes only. All subjects will have vital signs assessed before and after study drug injection for safety purposes (not as a research procedure). Histopathological assessment will be performed, as standard of care, on tissue obtained from either RP, with or without EPLND, or biopsy of either the primary lesion or presumed metastases, within two weeks of study drug dosing, where indicated; such standard of care data will be reviewed via chart review. All subjects will be followed via chart review for three years after their visit 1 scan. 68Ga-PSMA-HBED-CC image data will be evaluated for visible uptake and compared with histopathology. Both 68Ga-PSMA-HBED-CC PET and MRI (or CT) image data will be individually assessed for appropriate staging. In the event that subjects undergo focal therapy and are scheduled to receive a post-treatment MRI as standard of care, they will be asked to participate in an optional, second posttreatment visit performed the same way as visit 1 (pre-treatment MRI); a single IV dose of 68Ga-PSMA-HBED-CC (study drug) followed by a PET/MRI scan, 1-3 hours after injection. Please note, in the event that subjects undergoing focal therapy receive a PET/CT instead of a PET/MRI, they will not have the option of participating in a second visit.

INCLUSION AND EXCLUSION CRITERIA

INCLUSION CRITERIA

1. Male aged 21 years or older.
2. Ability to provide signed informed consent and willingness to comply with protocol requirements.
3. Pathologic confirmation of adenocarcinoma of the prostate gland or high clinical suspicion (PSA > 4 ng/mL, or PSA density > 0.15 ng/mL2, or PSA doubling time < 2 years).
4. Meet one of the following 5 Criteria:
 - a. Planned for surgical extirpation, which may or may not include lymph node dissection (high risk primary disease)
 - b. Planned for targeted biopsy of primary lesion
 - c. Conventional imaging equivocal or suggestive of prostate cancer metastasis/es
 - d. Planned focal therapy (with or without radiation therapy) with serial follow-up
 - e. Elevated PSA with no conventional imaging suggestive of metastatic or recurrent disease

5. a. If part of PET/MRI cohort, subject will undergo clinically indicated MRI imaging prior to treatment.
Or b. If part of PET/CT cohort, subject will have had clinically indicated MRI within 3 months prior to treatment.

6. Participants must agree to use an acceptable form of birth control throughout the study period. Participants must use condoms for a period of seven days after each injection, if engaged in sexual activity."

EXCLUSION CRITERIA

1. Clinical and/or technical factors that would compromise statistical analysis of the PET and/or MRI.
2. If part of PET/MRI cohort and patient cohort 3 or 5, subject does not plan to have a prescribed abdomen2/ MRI
3. If part of PET/MRI cohort and patient cohort 1, 2 or 4, subject does not plan to have a prescribed pelvis MRI
4. If part of PET/CT cohort and patient cohort 3 or 5, subject does not have previous MR imaging of abdomen and pelvis
5. If part of PET/CT cohort and patient cohort 1, 2 or 4, subject does not have previous MR imaging of pelvis
6. If part of PET/CT cohort, investigator review determines that previous MR images do not meet institutional quality standards
7. If part of PET/MRI cohort, contraindications to MRI
8. Contraindications to PSMA IV administration
9. Other unspecified reasons that, in the opinion of investigators, make the subject unsuitable for enrollment

DATA AND SAFETY MONITORING PLAN

Data is recorded both electronically and in paper format Data will be kept in the PIs locked office Data will be kept on a password-protected computer Data will be saved on a secure server.

The study will be stopped if there are any serious adverse events related to any of the study procedures, but this is not anticipated. However, subjects who experience an AE of grade 3 or higher will be reviewed and removed from the study. Vital signs will be obtained before and after the dose administration.

This study will follow standard operating procedures for reporting adverse events and utilize the AE grading from Terminology Criteria for Adverse Events v4.0. AE grading will be defined as the

following categories: Grade 1- Mild; asymptomatic or mild symptoms; clinical or diagnostic observations only; intervention not indicated. Grade 2- Moderate; minimal, local or noninvasive intervention indicated; limiting age-appropriate Activities of Daily instrumental Living. Grade 3- Severe or medically significant but not immediately life-threatening; hospitalization or prolongation of hospitalization indicated; disabling; limiting self care Activities of Daily Living. Grade 4- Life-threatening consequences; urgent intervention indicated. Grade 5- Death related to AE.

The primary endpoint is to assess the sensitivity and specificity on per-subject basis between the diagnosis from MRI and 68Ga-PSMA-HBED-CC. Based on the previous literature, we anticipate a 0.58 sensitivity and a 0.82 specificity that are consistent across all seven scenarios based on MRI. Here, we first assume that an increase in sensitivity of 30%, i.e. 0.75 under 68Ga-PSMA-HBED-CC will provide little benefit over existing MRI approach. Therefore, our statistical test for 68Ga-PSMA-HBED-CC sensitivity will be based on the null hypothesis of a value as 0.58 with the alternative hypothesis of at least 0.75. The sample size calculation is based on a Wald-test statistic under an arcsine transformation of proportion and an effective size 0.36. As a result, a sample of 34 true positive patients will give us 80% power to reject the null hypothesis at a onesided 0.1 significance level. In terms of specificity, we will expect a non-inferior performance from 68Ga-PSMA-HBED-CC compared with MRI. By assuming delta to be the estimated difference in the specificity between MRI and 68Ga-PSMA-HBED-CC, the statistical test for this metric will be constructed under the null hypothesis that the actual difference is larger than delta and the alternative hypothesis of that is smaller or equal to delta. The test statistic will asymptotically follow a normal distribution based on based on a restricted maximum likelihood estimation approach with the sample size obtained by a Wald-test statistic. Assuming delta=0.15, a sample of 12 true negative (TN) patients will allow us 80% power for this a one-sided 0.1 significance level test. In summary, we need a total of 46 patients (34 TP, 12 TN) for each scenario, leading to a total of 322 patients. Since we expect a 20% drop-off rate, we therefore intend to recruit 402 subjects. The sensitivity and specificity for the diagnosis under 68Ga-PSMA-HBED-CC and MRI on a per patient basis will be summarized as descriptive statistics and the two-sided 90% confidence intervals (CIs) will be constructed using the Wilson score method. The superior of 68Ga-PSMA-HBED-CC MRI for detection of metastatic prostate cancer will be determined if two of the three readers show statistically significantly better performance on sensitivity based on the McNemar test of discordant pairs for subjects and a non-inferiority specificity performance based on overlapped confidence intervals. The lesion-level data will be analyzed by McNemar's test adjusted for clustered data (each subject will contribute at least one lesion result, and possibly many lesion results). Published methods will be used for the lesion-level analyses (Durkalski et al, Statist. Med. 2003; 22:2417-2428 "Analysis of clustered matched-pair data"; Statist. Med. 2003; 22:279-290 "Analysis of clustered matchedpair data for a non-inferiority study design"). Reader-specific sensitivities and specificities will be calculated primarily for patient-based results for lymph nodes of any size. Sensitivity and specificity calculations will be performed for each imaging modality with the CIs calculated based on Wilson score method. In addition, we will assess 68Ga-PSMA-HBED-CC PET and MRI image data for cancer staging and compare their performance based on a Wilcoxon signed-rank test. And finally, safety of the 68Ga-PSMA-HBED-CC test will be assessed by tabulation of any procedure-related adverse effects.

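### In cohort 5, and possibly cohort 3, the reference standard is not fixed independently of the PET result, so the PET–MRI sensitivity comparison may be biased, towards PET in cohort 5 and in either direction in cohort 3

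*Combined protocol and SAP*

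**What the plan says.** **Reference standard.** The Study Design section compares PET with MRI "using histologic confirmation or serial follow-up for up to 3 years as the gold standard". Tissue is assessed as part of standard care, "within two weeks of study drug dosing, where indicated; such standard of care data will be reviewed via chart review". Follow-up is universal: "All subjects will be followed via chart review for three years after their visit 1 scan".

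**Cohort 3.** Study Design defines it as "Conventional imaging equivocal or suggestive of metastatic disease, with planned biopsy of presumed metastasis". The eligibility rule for the same group, inclusion 4c, reads only "Conventional imaging equivocal or suggestive of prostate cancer metastasis/es".

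**Cohort 5.** Study Design and inclusion 4e use the same description, "Elevated PSA with no conventional imaging suggestive of metastatic or recurrent disease". Neither mentions a tissue procedure.

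**Status of the scans and readers.** For PET/MRI, "the MRI portion is standard of care but the PET is for research only"; the PET/CT is likewise a research scan. On reading, "a panel of independent readers will evaluate the MRI and PET studies to assess the level of suspicion for prostate cancer". The panel reads images and is not described as setting the reference.

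**Analysis.** The statistical section makes per-subject sensitivity and specificity primary. It tests sensitivity by McNemar's test, requires success in two of three readers, and does not separate subjects by type of reference.

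**Not stated anywhere:**
- whether the PET result reaches the treating team
- which subjects are classified by histology and which by follow-up
- what makes a follow-up chart positive or negative
- whether the reference is set without sight of the PET

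**The concern.** A paired accuracy comparison is fair only if disease status is established in a way that does not depend on either test. In cohort 5 no lesion is suspected on conventional imaging at entry and no biopsy is planned, so a new biopsy target is quite likely to be one that the research PET shows. If such a finding leads to tissue, PET-positive disease is confirmed promptly. PET-negative disease becomes reference-positive only if routine care detects it within three years. Disease that PET misses and follow-up also misses leaves the sensitivity denominator and is counted among the reference-negatives. A second route needs no biopsy: whoever abstracts the chart may see the PET report and let it colour the truth call.

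Inclusion 4c may extend the problem to cohort 3, because a patient can enter without the planned biopsy that would have fixed verification before the scan. What is at stake is the superiority claim for sensitivity, and to a lesser degree the non-inferiority claim for specificity.

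**Working it through.** **1. The plan's own figures.** The statistical section gives sensitivity 0.58 under the null and 0.75 under the alternative, one-sided 0.1, 80% power. The arcsine effect is h = 2·asin(√0.75) − 2·asin(√0.58) = 0.363. Then n = (1.2816 + 0.8416)² / 0.363² = 34.2. The stated 34 reproduces, with power 79.8% at 34. The total is 7 × 46 = 322.

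**2. How much of the sample is exposed.** Scenarios 5a and 5b hold 2 × 46 = 92 of 322 (29%). Adding 3a and 3b gives 4 × 46 = 184 of 322 (57%), but for cohort 3 the direction is open (step 5).

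**3. Apparent sensitivity if histology follows PET.** The documents give no verification rates, so these inputs are assumptions:
- true sensitivity s = 0.58 for both tests, so PET has no real advantage
- PET and MRI reads independent given disease
- every PET-positive diseased subject is confirmed
- a share f of PET-negative diseased subjects is found on follow-up

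Apparent PET sensitivity = s / [s + (1 − s)f]. At f = 0.8 this is 0.58 / (0.58 + 0.42 × 0.8) = 0.58 / 0.916 = 0.633. MRI stays at 0.58 because its reads are independent of PET.

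**4. Effect on the McNemar test.** At f = 0.8 the discordant cells among apparent positives are:
- PET+/MRI−: 0.58 × 0.42 / 0.916 = 0.266
- PET−/MRI+: 0.42 × 0.58 × 0.8 / 0.916 = 0.213

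The table gives the exact rejection probability of the asymptotic test, taken as one-sided 0.1 to match the sample-size calculation, for one reader with 34 apparent positives.

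| f | PET | MRI | False-positive rate |
|---|---|---|---|
| 1.0 | 0.580 | 0.580 | 0.105 |
| 0.9 | 0.605 | 0.580 | 0.148 |
| 0.8 | 0.633 | 0.580 | 0.209 |
| 0.7 | 0.664 | 0.580 | 0.292 |
| 0.5 | 0.734 | 0.580 | 0.534 |

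With correlation 0.4 between reads, MRI is carried up too. At f = 0.8 the result is PET 0.633, MRI 0.601, rate 0.172. At f = 0.5 it is 0.734, 0.642 and 0.397.

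**5. Other routes to histology** (f = 0.8, independent reads).
- Histology follows MRI: PET 0.580, MRI 0.633, rate 0.045. The bias reverses.
- Either positive scan leads to histology: both 0.601, rate 0.104. No relative bias.
- Neither scan drives histology: both 0.580, rate 0.105.

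**6. Specificity.** Take 34 diseased and 12 disease-free subjects, both specificities 0.82 (for PET an assumption), and the model of step 3 with f = 0.8. Missed disease is 34 × 0.42 × 0.2 = 2.856 subjects, all PET-negative and 42% MRI-negative.
- PET: (9.84 + 2.856) / 14.856 = 0.855
- MRI: (9.84 + 1.200) / 14.856 = 0.743

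The gap is 0.11 against the plan's delta of 0.15. The rise in PET specificity depends on confirming every PET-positive case. If 90% of PET-positive and 40% of PET-negative disease is confirmed, the unconfirmed shares are 0.58 × 0.10 = 0.058 and 0.42 × 0.60 = 0.252. Then 0.252 / 0.310 = 81.3% are PET-negative, just under 0.82, and PET specificity falls slightly. MRI specificity falls more (58% of these subjects are MRI-positive), so a relative effect remains.

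**The case against.** The strongest reply is that PET-driven biopsy is nowhere written. The PET is labelled research only and histology standard care, which can be read as meaning that the scan does not steer management. Every subject also has three years of chart follow-up, which is itself part of the reference. This stands in part. It rules out saying that PET does drive biopsy. It does not establish that PET cannot, because the research label distinguishes the PET from the standard-of-care MRI and says nothing about disclosure. The chart review has no stated imaging schedule and no definition of disease, so complete ascertainment cannot be assumed.

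A second reply stands fully for cohort 3. Those patients enter because conventional imaging is equivocal or suggestive, so they have a biopsy target before the PET, and verification led by conventional imaging could favour MRI.

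A third also stands. Cohort 5 is entered on negative conventional imaging. If that includes the MRI under study, which the documents do not say, 0.58 is not a suitable MRI sensitivity there, and step 3 shows the mechanism rather than forecasting the result.

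A reader might infer that PET sensitivity is inflated in all four of scenarios 3a, 3b, 5a and 5b, or that verification alone would produce the hypothesised gain from 0.58 to 0.75. The documents support neither. The first treats silence on disclosure as fact and ignores the direction problem in cohort 3. The second needs verification rates that the documents do not supply.

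**Conclusion.** The point holds as an uncontrolled risk. In cohort 5, and possibly in cohort 3 through the gap between Study Design and inclusion 4c, the choice between histology and follow-up is not fixed independently of the PET, and nothing keeps the PET report out of the reference call. PET sensitivity may be inflated relative to MRI in cohort 5; in cohort 3 the sign is open.

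The size cannot be derived from the documents. Under the assumptions of step 3, with follow-up finding 80% of unbiopsied disease, two equally sensitive tests would differ by about 0.05 and the single-reader error rate would roughly double. The bias vanishes in this model if follow-up finds all disease, and no term favouring PET arises if biopsy does not depend on PET. The error rates are per reader; the rate under the two-of-three rule depends on agreement between readers, which the plan does not give. The point merits action because analysis cannot fully repair a reference standard if nobody recorded how it was set.

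**What to change.** 1. Reconcile the cohort 3 definition in Study Design with inclusion 4c. Which version applies is for the sponsor to decide. This does nothing for cohort 5, so the next two steps are needed regardless.
2. Set each subject's reference status from a chart extract with the research PET report removed. State that no PSMA PET finding, from the study or later, counts by itself as confirmation. Record whether the PET result was available to the treating team and whether it prompted the biopsy; redaction alone would leave a PET-prompted biopsy result in the chart with its origin hidden.
3. In cohorts 3 and 5, report PET and MRI sensitivity and specificity, with the McNemar comparison, separately for histology-verified and follow-up-verified subjects. Qualify the superiority conclusion if the two disagree.

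A Begg–Greenes correction conditioning on both calls is optional. It needs enough verified subjects who are negative on both scans, and with 46 per scenario cohort 5 may have too few.

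Cost: some abstraction work, two recorded items and one extra table, with no added biopsy or reader and no change to the 34 positives per scenario. The strata will be less precise than the pooled result, and the apparent PET advantage may shrink.

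### The 80% power for sensitivity belongs to a one-sample test against a fixed 0.58, not to the two-of-three-reader McNemar rule that decides superiority

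*Combined protocol and SAP*

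**What the plan says.** All the sizing and decision text is in the unnumbered statistical section at the end of the combined protocol and SAP.

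- **Sizing test.** The plan states that "our statistical test for 68Ga-PSMA-HBED-CC sensitivity will be based on the null hypothesis of a value as 0.58", against an alternative of at least 0.75. It uses a Wald statistic on the arcsine scale with effect size 0.36 and concludes that "a sample of 34 true positive patients will give us 80% power to reject the null hypothesis at a onesided 0.1 significance level". The 0.58 is the literature value anticipated for MRI.
- **Deciding rule.** Superiority holds "if two of the three readers show statistically significantly better performance on sensitivity based on the McNemar test of discordant pairs for subjects". The same sentence attaches a second requirement, on specificity, which the plan judges only by whether the PET and MRI intervals overlap.
- **Scope.** The superiority sentence concerns PET "for detection of metastatic prostate cancer will be determined". The sample is built scenario by scenario: "we need a total of 46 patients (34 TP, 12 TN) for each scenario, leading to a total of 322 patients".
- **Design.** Study Design calls this a "paired, case-control design that is appropriate to statistically evaluate the difference in sensitivity and specificity between the two imaging modalities". Its cohorts include primary-lesion questions, for example cohort 2: "Presumed intermediate or high-risk primary disease with planned targeted prostate biopsy".

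The plan gives no PET-MRI discordance rate, between-reader correlation or McNemar power.

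**The concern.** One primary sensitivity hypothesis has two tests attached to it. The first treats MRI sensitivity as a known constant and has no term for discordant pairs, sampling error in MRI, or readers. The second compares PET with the MRI reads actually obtained, patient by patient, three times over. Only the first was powered.

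The power of the second depends on four things the plan leaves open: how often PET and MRI disagree in diseased patients, how strongly the readers agree, whether McNemar's test is asymptotic or exact, and whether the rule is applied within each scenario or pooled. The McNemar sentence does not state its alpha either; one-sided 0.1 appears only with the sizing tests.

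The sensitivity calculation accounts for 34 × 7 = 238 of the 322 evaluable patients. With the test form, alpha and unit of analysis open, those choices could be made after the data are seen, and the two named tests can give different answers on the same data.

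**Working it through.** **1. Reproduce the plan's figure.** Inputs from the statistical section: 0.58, 0.75, one-sided 0.1, 80% power.

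- h = 2·asin(√0.75) − 2·asin(√0.58) = 0.3629, which the plan rounds to 0.36.
- n = (1.2816 + 0.8416)² / h² = 34.2. Power at n = 34 is 79.8%.

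Other forms do not give 34: the two-sided one-sample version needs 47, and the two-sample arcsine version needs 69 per group. The 34 is therefore a one-sided, one-sample calculation.

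**2. Range of discordance.** Let ψ be the proportion of diseased patients in whom PET and MRI disagree. The documents do not give it, but the sensitivities bound it.

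- Minimum: 0.75 − 0.58 = 0.17.
- Independent reads: 0.75 × 0.42 + 0.58 × 0.25 = 0.46.
- Maximum: 0.42 + 0.25 = 0.67.

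**3. One reader, n = 34, one-sided 0.1 (assumed for McNemar), full enumeration.** The number of discordant pairs is m ~ Bin(34, ψ). The number favouring PET is b | m ~ Bin(m, (ψ + 0.17)/(2ψ)), and c = m − b. Reject if (b − c)/√m ≥ 1.2816 (asymptotic) or if P(B ≥ b | m, 0.5) ≤ 0.1 (exact).

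| ψ | Asymptotic | Exact |
|---|---|---|
| 0.17 | 98.6% | 85% |
| 0.23 | 85% | 70% |
| 0.25 | 81% | 67% |
| 0.30 | 73% | 61% |
| 0.40 | 63% | 52% |
| 0.46 | 59% | 48% |

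**4. Two-of-three rule, n = 34, by simulation.** There were 40,000 trials per cell. Assumptions: all three readers share sensitivities 0.58 and 0.75; reads come from a latent-normal model with the PET-MRI correlation solved for each ψ; between-reader correlation is 0.5 to 0.8 on the latent scale (not kappa); cross-reader PET-MRI correlation is the product of the two.

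| ψ | Asymptotic | Exact |
|---|---|---|
| 0.20 | 96-97% | 82-84% |
| 0.23 | 90-92% | 74-76% |
| 0.25 | 86-88% | 71-73% |
| 0.28 | 80-82% | 66-68% |
| 0.30 | 77-79% | 63-65% |
| 0.33 | 72-75% | 59-61% |
| 0.40 | 66-67% | 52% |
| about 0.46 | 61-62% | 47-48% |

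Power reaches 80% only if ψ is at or below about 0.28-0.29 (asymptotic) or about 0.21 (exact). A second cross-reader structure, using the smaller of the two correlations, adds at most about 4 points and moves these limits to at most 0.31 and 0.22.

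**5. What these figures leave out.** They cover the sensitivity component only, and the specificity condition can only lower joint power. For scale: with one reader, 12 patients, both specificities 0.82, independent reads and 90% Wilson intervals, the PET upper limit reaches the MRI lower limit in 99.5% of trials. The overlap condition as written would therefore cost little.

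**6. Pooled readings (one reader, one-sided 0.1).**

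- All seven scenarios, 34 × 7 = 238: 99.6% asymptotic and 99.5% exact at ψ = 0.46; 97.5% and 97.0% at the extreme of 0.67.
- Only 3a, 3b, 5a and 5b, taken here as the metastatic-question scenarios, 34 × 4 = 136: 99.5% and 99.2% at ψ = 0.30; 95.7% and 94.2% at 0.46.

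**The case against.** **The deciding rule is stated, and the 0.58 text is only planning.** The superiority sentence does say how superiority will be determined, and one-sample sizing is a common shortcut. But the plan does not call it a shortcut; it presents the fixed-0.58 comparison as the statistical test. Even on the kinder reading, the 80% was not computed for the rule that decides.

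**Power may be fine.** This stands in part. At low discordance the per-scenario rule exceeds 80%. If the rule is pooled over all scenarios, or only over those asking about metastases, sensitivity power is about 94% or more up to independence. The shortfall arises only on the per-scenario reading. That reading fits the way the sample is built, but the plan does not say the decision is made that way. Pooling all seven sits awkwardly with a claim limited to metastatic disease, since cohorts 2 and 4 concern primary lesions.

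**The alpha is assumed.** This is true. One-sided 0.1 is the only test level the plan states, so it was used. The plan's two-sided 90% intervals would correspond to one-sided 0.05. At that level single-reader power at n = 34 is 80% asymptotic and 62% exact at ψ = 0.20, and 60% and 45% at 0.30. This strengthens the case for stating the level.

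**Conclusion.** The concern holds. The 80% is the power of a one-sample test against a known 0.58, and the plan gives no power for the paired two-of-three-reader rule that determines superiority. On the per-scenario reading, the sensitivity component of that rule runs from about 97% (ψ = 0.20, asymptotic) to about 47% (independent reads, exact). This assumes true sensitivities of 0.58 and 0.75 in every reader, one-sided 0.1 and latent between-reader correlation of 0.5 to 0.8.

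This does not show the trial to be underpowered. It shows that the stated power is not established for the primary claim, and that test form, alpha and unit of analysis need fixing before the data are read. The correction is needed because the point concerns the primary decision and the only justification given for the diseased-patient sample.

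**What to change.** Name the two-of-three McNemar rule as the single primary sensitivity test. Remove the fixed-0.58 test, or label it a planning approximation. Then state:

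1. whether McNemar's test is asymptotic or exact;
2. that its level is one-sided 0.1;
3. whether the rule applies within each scenario or pooled, over which cohorts, and how this fits a claim about metastatic disease;
4. the assumed range of PET-MRI discordance and its basis;
5. the assumed range of between-reader correlation, and the scale it is on.

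Replace the unconditional 80% with the power range of the two-of-three rule over items 4 and 5, at n = 34 or at the pooled n if item 3 says so. Label it as the sensitivity component and not the joint rule.

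**Cost.** Wording only, with no extra patients, if the sponsor accepts the resulting range. The stated per-scenario power will be lower if discordance is moderate or the exact test is chosen. For information only: holding 80% per scenario would take about 38 (asymptotic) or 50 (exact) diseased patients at discordance 0.30, 55 or 65 at 0.40, and 65 or 75 at about 0.46. These come from a coarse simulation grid (steps of 5 above 45).
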